Currently, procalcitonin concentration is measured in all surgical ICU patients for whom a BAL is sent on the day of the BAL as part of a separate non-interventional study. For the purposes of the current trial, procalcitonin concentration will also be measured during treatment in order to assess response, as well as following treatment in order to assess for recurrence. Because study entry will occur at the time that VAP is confirmed microbiologically (approximately 72 hours following the BAL and initiation of empiric antibiotics), these measurements will begin after three days of antibiotic therapy. Procalcitonin concentration will then be measured daily for the remainder of treatment, as well as daily for 72 hours following treatment. Thus, the 4 day group will have procalcitonin concentration measured at baseline, treatment days 3 and 4, and post treatment days 1-3. The 8 day group will have procalcitonin measured at baseline, treatment days 3-8, and post-treatment days 1-3. The treatment team will have access to the results of these measurements. For the purposes of the trial, biomarker resolution will be defined as a procalcitonin concentration $< 0.5 \mu\text{g/L}$ or a decrease of $\geq 80\%$ relative to the day of the BAL [26].

Additional Outcomes: Days of antibiotics, antibiotic days (defined as the product of days of antibiotics and number of antibiotics per day), recurrence, ventilator days, empyema, need for tracheostomy, non-pulmonary infections, ICU length of stay (LOS), hospital LOS, and mortality. Recurrence is defined using the same clinical and microbiologic criteria as the initial episode of VAP, and occurring 2-14 days

following completion of initial therapy. Relapse is defined as recurrent VAP caused by the initial pathogen; super-infection is defined as recurrent VAP caused by ≥ 1 new pathogen. VAP occurring > 14 days following completion of initial therapy will be considered a second episode of pneumonia as opposed to a recurrence. The incidence of recurrent VAP due to a MDR pathogen, as well as any other infection caused by a MDR pathogen, will also be abstracted.

Baseline Variables: Age (years), gender, admission diagnosis, associated diagnoses, admission APACHE II score, comorbidity index [27], prior and current antibiotic exposure, base deficit, serum lactate concentration, time from ICU admission to BAL, presence of organisms on gram stain, and presence of polymorphonuclear lymphocytes on gram stain.

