Sample acquisition and processing: The default method for BAL specimen acquisition will be via the blind or “mini” BAL technique [18], using an 85 mm by 4 mm bronchial diagnostic catheter (Combicath, ® Prodimed, Neuilly-en-Thelle, France). The catheter is passed through the artificial airway until resistance is met. It is then withdrawn approximately 1 cm and the inner lavage catheter is deployed. Lavage is then performed with 20 – 40 mL of sterile saline.

The BAL will be obtained bronchoscopically if bronchoscopy is being performed for another indication (e.g., pulmonary toilet, percutaneous dilational tracheostomy). Lavage is performed using 20-40 mL of normal saline lavage into the lobar bronchus that appears most abnormal on CXR.

Using a 0.001 calibrated loop, vortexed BAL specimens will be plated onto sheep blood, MacConkey, and Chocolate agar at 35°C - 37°C in CO₂. Plates will be examined after 24, 48, and 72 hours prior to issuing a final negative report. 100 or more colonies per plate is considered significant and represents $\geq 10^5$ cfu/mL.

Statistical Analyses:

Power analysis: Power analysis was performed using SAS Version 9.1 (SAS, Inc., Carey, NC, *proc power*). The Analysis was based on a non-inferiority study design, defined as a difference in outcomes between the 4 day and 8 day groups of < 10%. Furthermore, as the intention was to show non-inferiority, tests were one-sided using an alpha error level of 0.10. The beta error level was set at 0.20 for 80% power. Analysis for the outcome of VAP recurrence returned the largest sample size. From 2010-2012, during which time VAP was treated with ≥ 8 days of therapy, the incidence of recurrent VAP in the DHMC surgical ICU was approximately 25%. Projecting a recurrence rate after 4 days of treatment of 35% returns a total sample size of 103..

Interim Analysis: An interim analysis will be conducted for all outcomes after 50% accrual (n_{total}=50).

Data Analysis: Data analyses will be performed using SAS Version 9.1 (SAS, Inc., Carey, NC). Data will be analyzed using an intention-to-treat strategy (i.e., patients randomized to receive 4 days of antibiotic therapy will be analyzed with this group even if they receive longer courses). Data will be expressed as median (range) or number (%). Normality of continuous variables will be assessed using the

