Kolmogorov-Smirnov test. Differences in the means of continuous variables that are distributed normally will be assessed using the Student's t-test. Differences in the medians of continuous variables that are not distributed normally will be assessed using the Wilcoxon Rank Test. Proportions of categorical variables will be compared using the chi-squared test. When expected cell counts are < 5, Fischer's exact test will be used. Univariate analysis of categorical outcomes will be expressed as the relative risk with 95% confidence intervals. A logistic regression model will be fit to address possible confounding by differences in baseline parameters between groups. Baseline variables associated with randomization status at the $p<0.25$ level by univariate analysis will be added to the model using a forward selection method. The overall contribution of the fitted model to predicting variability in the outcome of interest will be assessed using the likelihood ratio chi-squared test. The independent contribution of individual variables will be assessed using the Wald chi-squared test. Model fit was will be assessed using the Hosmer-Lemeshow goodness-of-fit chi-squared statistic, with $p>0.05$ indicating acceptable model calibration. The alpha error level is defined at 0.05, with statistical significance set at $p<0.05$.

Adverse Event Monitoring and Reporting: Adverse event monitoring will occur daily. The safety of the study will be monitored by an independent, external Data Safety Monitoring Board, consisting of a medical intensivist, and an infectious disease physician. The committee will meet biannually and submit written reports to the IRB.

References:

1. Edwards, J.R., K.D. Peterson, Y. Mu, S. Banerjee, K. Allen-Bridson, G. Morrell, et al., National Healthcare Safety Network (NHSN) report: data summary for 2006 through 2008, issued December 2009. *Am J Infect Control* 2009;37:783-805
2. Neu, H.C., The crisis in antibiotic resistance. *Science* 1992;257:1064-73
3. Mahgoub, S., J. Ahmed, and A.E. Glatt, Completely resistant *Acinetobacter baumannii* strains. *Infect Control Hosp Epidemiol* 2002;23:477-9
4. Kollef, M.H. and V.J. Fraser, Antibiotic resistance in the intensive care unit. *Ann Intern Med* 2001;134:298-314
5. Bradley, J.S., R. Guidos, S. Baragona, J.G. Bartlett, E. Rubinstein, G.G. Zhanel, et al., Anti-infective research and development--problems, challenges, and solutions. *Lancet Infect Dis* 2007;7:68-78

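### The additional outcomes share one unrestricted p<0.05 rule with no error control or exploratory status, giving roughly a 15–30% chance of a false significant result among the seven listed and 18–43% if eleven are tested

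*Combined protocol and SAP*

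**What the plan says.** The Outcomes section names two main outcomes: effectiveness of treatment (assessed clinically, microbiologically and by biomarker) and antibiotic exposure. The Additional Outcomes paragraph then gives two exposure measures (days of antibiotics and antibiotic days), followed by "recurrence, ventilator days, empyema, need for tracheostomy, non-pulmonary infections, ICU length of stay (LOS), hospital LOS, and mortality".

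The same paragraph defines relapse and super-infection as types of recurrence. It ends by saying that data will be abstracted on two resistance items: "The incidence of recurrent VAP due to a MDR pathogen, as well as any other infection caused by a MDR pathogen".

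The Data Analysis section assigns tests by type of variable: t-test or Wilcoxon for continuous variables, chi-squared or Fisher's exact for categorical ones. It promises relative risks with 95% confidence intervals for categorical outcomes and closes with one threshold: "The alpha error level is defined at 0.05, with statistical significance set at" p<0.05. Nothing limits that threshold to particular outcomes. No multiplicity adjustment, order of testing or exploratory label appears anywhere.

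The Power analysis uses a different level: "tests were one-sided using an alpha error level of 0.10". It takes the sample size from recurrence.

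**The concern.** Taken literally, the plan lets any additional outcome with p<0.05 be reported as statistically significant. With seven or more such comparisons in a trial sized on recurrence alone, an isolated significant result is quite likely to be chance. It could fall either way: a spurious gain in ventilator days or length of stay for the short course, or a spurious harm.

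The Background justifies the trial by the emergence of resistant pathogens. A chance result on a resistance outcome, if those are tested, could therefore be given more weight than the design supports.

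**Working it through.** **The plan's own figures.** The documents state no family-wise error rate, so there is none to reproduce. The only computed design figure is the total of 103. It does not come back as a two-arm size at one-sided 0.10 and 80% power: non-inferiority with both rates at 25% and a 10-point margin gives 340, and 25% vs 35% tested for superiority gives 378. That is a separate matter. Here 103 serves only to set the arm sizes (52 and 51).

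**Counting the outcomes** (Additional Outcomes paragraph)
- The paragraph lists ten: two exposure measures plus eight others.
- Remove the two exposure measures. They measure a main outcome and are expected to differ by design.
- Remove recurrence, which sets the sample size.
- Seven remain: ventilator days, empyema, tracheostomy, non-pulmonary infections, ICU stay, hospital stay and mortality.
- Adding relapse, super-infection, recurrent MDR pneumonia and other MDR infection gives 7 + 4 = 11.

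**Inputs**
- Per-test level: 0.05, from Data Analysis. Sidedness is not stated; two-sided is assumed.
- Number of tests: k = 7 or 11, from the count above.
- Correlation between test statistics: not in the documents. A common value from 0 to 0.8 is assumed.
- One final analysis. The planned interim look is left out.

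**Independent tests.** P(at least one false positive) = 1 − 0.95^k.
- k = 7: 1 − 0.6983 = 0.302
- k = 11: 1 − 0.5688 = 0.431

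**Correlated tests.** Simulation of k equicorrelated normal statistics, 200,000 draws, counting draws in which any |z| exceeds 1.96:

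| Correlation | 7 tests | 11 tests |
|---|---|---|
| 0 | 30% | 43% |
| 0.3 | 27% | 37% |
| 0.5 | 23% | 30% |
| 0.8 | 15% | 18% |

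The expected number of false positives does not depend on correlation: 7 × 0.05 = 0.35, or 11 × 0.05 = 0.55. Correlation only bunches them into fewer trials.

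**Rare events.** The planned chi-squared/Fisher rule at 51 vs 52 patients has an exact size of 0.0148 at an assumed 5% event rate, 0.035 at 10% and 0.050 at 25%. If one of the seven outcomes (say empyema) occurs in 5% and the tests are independent, the rate is 1 − 0.95^6 × 0.9852 = 1 − 0.7351 × 0.9852 = 0.276, against 0.302. If three of eleven are that rare, it is 1 − 0.95^8 × 0.9852^3 = 0.366, against 0.431.

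**Planned tests simulated at 52 vs 51.** Event rates are assumed, with relapse, super-infection and recurrent MDR pneumonia nested inside a 25% recurrence rate. The seven listed outcomes give 17–27% and all eleven give 24–34%, over latent correlations of 0.8 to 0. The lower ends exceed 15% and 18% because a latent correlation of 0.8 between yes/no outcomes produces a weaker correlation between their test statistics.

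**The case against.** Several objections have force, and they set the limits of the point.

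- **Are all eleven tested?** A reader might infer that eleven outcomes, including the resistance outcomes, are each tested at 0.05. The documents do not say so. Relapse and super-infection appear only as definitions. The resistance items are only to be abstracted, which describes data collection. Testing them is an inference from the general rule. The firm count is seven.
- **Is there no hierarchy at all?** A reader might infer that additional outcomes stand level with the main ones. The split between main and additional outcomes is a ranking of sorts. What is missing is any consequence for inference: the threshold is the same in both tiers, and nothing controls error within the lower one.
- **Can one figure be quoted?** About 30% fits eleven tests at correlation 0.5, and equally seven independent tests. The documents supply no correlation, so only a range is supported.
- **Is non-significance on mortality or empyema liable to be read as safety?** That is a matter of power, not multiplicity, and is not part of this point. The promised relative risks with 95% confidence intervals already give some protection for categorical outcomes.
- **Does it matter to the main result?** The conclusions on effectiveness and exposure are unchanged.

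What remains is that the rule, followed as written, permits unprotected claims of significance across the additional outcomes.

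**Conclusion.** The point holds as a minor one. At the final analysis, with no true differences, the chance of at least one false significant result is three to six times the nominal 0.05 for the seven listed outcomes (0.15/0.05 to 0.30/0.05). It is about 3.6 to 8.6 times if eleven are tested (0.18/0.05 to 0.43/0.05). These figures rest on two-sided tests, a common correlation between 0 and 0.8, and normal statistics. Conservative tests on rare events reduce the upper ends to roughly 27% and 34% under the assumed event rates. Even the narrowest count with strong correlation stays well above 5%.

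**What to change.** In Data Analysis, replace the unrestricted threshold with wording along these lines: *Claims of statistical significance will be confined to the two main outcomes (effectiveness of treatment and antibiotic exposure) and to VAP recurrence. All other additional outcomes, and the MDR outcomes, are exploratory; each will be reported as a between-arm difference or relative risk with a 95% confidence interval, without a claim of significance.*

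The alpha for the retained comparisons must be settled at the same time, because Data Analysis gives 0.05 and the Power analysis gives one-sided 0.10. The new sentence should cite whichever level results from that reconciliation.

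A gated confirmatory test of an MDR outcome is not advised. The plan names no single main comparison whose success could open the gate.

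The cost is one or two sentences and no new data. The downside is that the sponsor can no longer call a difference in an individual additional outcome significant.
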